#### 4.8 Off Study Criteria

- 4.8.1 Progression of disease- Once patients demonstrate progression of disease at follow up MRI or CT or PET-CT scans at 3 or 6 months, other therapies may be offered (but are not considered part of this study). Disease progression is defined by radiographically visible nodules greater than 1.5 cm. However, patients would be followed until death even after the 6 month follow-up by notification by primary oncologist.
- 4.8.2 Voluntary withdrawal
- 4.8.3 Non-compliance with follow-up scheme
- 4.8.4 At the time of cytoreductive surgery if patients are found to have disease which cannot be debulked to a diameter <1 cm in aggregate will be taken off study and not given the perfusion treatment.

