### 1.0 Primary objectives of the study

**Primary objective 1:** To determine the efficacy of HIPEC using hyperthermic cisplatin given as a continuous perfusion after complete abdominal tumor excision in patients with DSRCT.

**Primary objective 2:** To determine the morbidity of extensive tumor resection and HIPEC on patients with DSRCT and other non-carcinoma tumors with extensive abdominal disease.

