## 4.2 Response Criteria and Statistical Considerations

4.2.1 This is a phase II study of continuous hyperthermia peritoneal perfusion (HIPEC) in patients with desmoplastic round cell tumor (DSRCT) and non-DSRCT patients. The primary objective is to assess the efficacy of this treatment, with a primary endpoint of time to relapse. The historical median time to relapse for DSRCT patients without HIPEC treatment was about 1.6 months. A maximum of 22 patients will be enrolled in MDACC at an estimated accrual rate of 1 patient every 2 months including a total of 5 non-DSRCT patients. Patients will be followed up until relapse, death or for 6 months after the treatment, whichever ever occur first. It would be encouraging if the median time to relapse could increase to 3.2 months with the HIPEC treatment. The toxicity and efficacy will be monitored during the study, and all the data will be used to update the prior distributions for toxicity and efficacy parameters. The study will be stopped for toxicity and futility based on the following stopping rules.

4.2.2 The primary endpoint TTP will be monitored using the method of Thall et al. (23). Denote median (TTP) =  $m_H$  for patients without HIPEC treatment and  $m_E$  for patients with HIPEC treatment. We assume that TTP is distributed exponentially with mean of  $m_H$  and  $m_E$ , respectively, in patients without and with HIPEC treatment. Under a Bayesian model, we will further assume that  $m_H$  has an inverse gamma (IG) prior with parameters (16.2, 24.3), with a mean of median TTP=1.6 months and variance = 0.18. We also assume that  $m_E$  follows IG prior (2.03, 1.64) with the same median TTP as  $m_H$  but with a much larger variance (100) to reflect much greater uncertainty about TTP in patients with HIPEC treatment. The TTP data will be monitored continuously, and the study will be terminated early if  $\Pr(m_H + d < m_E \mid \text{data}) < 0.05$ , where  $d = 1.6$  month. Specifically, the trial will be stopped early if, given the current data, there is less than 5% chance that the median TTP will improve by more than 1.6 month in patients treated with HIPEC, compared to those without HIPEC treatment. The operating characteristics of this decision rule are summarized in [Table 1](#).

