4.4 Re treatment criteria

4.4.1 If patients return with recurrent measurable disease and experienced a 6 month disease free interval since the last HIPEC, they will be offered a reperfusion when there is radiographic evidence of recurrent intra-abdominal disease and no new contraindications. Patients having a reperfusion will be treated with 50 mg/M of cisplatin. (This is based on renal insufficiency seen in 2 patients who underwent 2 perfusions at 100 mg/M)

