4.4.2 Patients who progress will be offered other treatment alternatives

- 4.5 On study evaluation
  - 4.5.1 Patients will undergo laboratory tests, imaging and physical exam as per on study criteria.
  - 4.5.2 During HIPEC patients will have continuous core temperature monitoring by the esophageal probe and bladder probe. Peritoneal temperature is measured every 10-15 minutes by up to eight probes placed either beneath the peritoneal surface or at the influx and efflux catheters. If the temperatures are increasing above 40°C ( $\pm 1$ ), the temperature of the perfusate will be reduced. If the temperature readings are too low, the emphasis of the manual agitation will be redirected to that area of the abdomen.
  - 4.5.3 Patients will be followed postoperatively with daily CBC, sodium, potassium, chloride, carbon dioxide, BUN, creatinine, AST, ALT, calcium, albumin, magnesium, phosphorous, total bilirubin, alkaline phosphatase, amylase for 5 +/-2 days and then twice weekly until discharge; and post-discharge at day 14 +/-3 days and day 30 +/- 3 days and at 3 and 6 month (+/- 2 weeks) follow-up (Appendix 1) Adverse events will be assessed on the same timetable.
  - 4.5.4 Patients will be monitored in the PICU no less than 48 hours. If necessary, adult patients will be admitted to ICU.
  - 4.5.5 Evaluation of measurable disease will be performed one month, 3 months and 6 months postoperatively (+/- 2 weeks) using CT or MRI and physical exam. (CT or MRI scan performed only at 3 and 6 months)
  - 4.5.6 Audiology evaluation will also be performed at one month evaluation.
- 4.6 Concurrent Therapies
  - 4.6.1 Patients will be allowed to proceed with any post-operative chemotherapy including allogeneic or autologous bone marrow transplantation. No concurrent medications will be given at the time of study drug administration since this is only a 90 minute period in the operating room. However, baseline medications and all medications through the 30 days follow up will be entered into PDMS/CORe.
- 4.7 Pharmacokinetics (Optional)
  - 4.7.1 Blood and peritoneal fluid samples (2.0 ml) will be collected in purple top tubes, centrifuged, and supernatant or plasma collected and stored at -20°C until analyzed.
  - 4.7.2 Blood and peritoneal fluid will be collected prior to the start of cisplatin-HIPEC and then at times 0, 30, 60 and 90

minutes. An additional blood sample will be collected 24 hours (+/- 8 hours) after the start of HIPEC.

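### The plan's only progression rule ignores nodules up to 1.5 cm, so a small new nodule at month 3 is not a relapse and its event can be dated late or lost

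*Combined protocol and SAP*

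**What the plan says.** Section 4.2.1 states the efficacy assessment "with a primary endpoint of time to relapse", and 4.2.2 then calls the same quantity TTP. Neither section says what counts as relapse. The one operational definition is in 4.8.1, among the reasons for leaving the study: "Disease progression is defined by radiographically visible nodules greater than 1.5 cm". It has no separate rule for new lesions and names no anatomical site.

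Section 4.5.5 sets evaluations at one, three and six months, each within two weeks, but limits imaging: "CT or MRI scan performed only at 3 and 6 months". For the endpoint, 4.2.1 says "Patients will be followed up until relapse, death or for 6 months after the treatment", whichever comes first.

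On disease at time zero, primary objective 1 concerns cisplatin "given as a continuous perfusion after complete abdominal tumor excision in patients with DSRCT", while 3.1.2 accepts residual nodules up to 1 cm thick. Section 4.4.1, on a second perfusion, begins "If patients return with recurrent measurable disease" and asks for radiographic evidence of recurrence in the abdomen, with no size.

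The yardsticks are in 4.2.1: "The historical median time to relapse for DSRCT patients without HIPEC treatment was about 1.6 months" and "It would be encouraging if the median time to relapse could increase to 3.2 months with the HIPEC treatment".

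**The concern.** After excision to 1 cm or less, a nodule that was not there before is a relapse in the ordinary sense. Under 4.8.1 it is not an event until it passes 1.5 cm. A patient with a new 1.2 cm nodule at month 3 counts as relapse-free, and the next scheduled look is month 6. The same patient could be recurrent under 4.4.1 and progression-free under 4.8.1.

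If that nodule has passed 1.5 cm at month 6, the recorded time is 6 months instead of 3. Those 3 extra months are nearly twice the 1.6-month improvement the trial looks for (3 / 1.6 = 1.9). If it has not, the patient is censored and the event disappears. Section 4.6.1 allows any post-operative chemotherapy, so a small nodule could also shrink and never be counted. At stake is the reported median, which will be read against 1.6 and 3.2 months.

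**Working it through.** **The plan's own figures.** The documents do not quantify the effect of the size rule. The nearest figure is Table 1, the early-stopping probabilities of the 4.2.2 rule: 0.998, 0.775, 0.178 and 0.126 at true medians of 1, 1.6, 3.2 and 4 months. I simulated the rule as written, with the inverse gamma parameter as the exponential mean, 20 patients, fixed accrual, a 6-month cap and checks at events. This gave 0.993, 0.763, 0.268 and 0.200. The 1.6-month row is close and the table as a whole is not reproduced. That is a separate matter, and nothing below rests on it.

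**Inputs from the documents.** Median 1.6 months and exponential times (4.2.1, 4.2.2); scans at months 3 and 6 (4.5.5); follow-up to 6 months (4.2.1); threshold 1.5 cm (4.8.1).

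**Assumptions.** A share f of the relapses present at a scan measure 1.5 cm or less. The documents give no nodule sizes, so f is shown over a range. Scans fall exactly on schedule, there are no unscheduled scans, and deaths are ignored.

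**Step 1, relapse present at each scan.**
- By month 3: 1 − 0.5^(3/1.6) = 72.7%
- By month 6: 1 − 0.5^(6/1.6) = 92.6%

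**Step 2, Kaplan-Meier median.** Recorded relapse at month 3 is 72.7% × (1 − f). It falls below one half when f exceeds 1 − 0.5/0.727 = 31.3%. Below that share the recorded median is 3 months; above it, the median moves to month 6 or later.

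**Step 3, exponential estimate of the median.** This is ln 2 × (mean recorded time) / (proportion with an event).
- Mean recorded time: 3 × 0.727(1 − f) + 6 × [1 − 0.727(1 − f)]
- Events, case A (nodules small at month 3 exceed 1.5 cm by month 6): 0.926 − (0.926 − 0.727) × f
- Events, case B (they do not, and are censored): 0.926 × (1 − f)

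| f | Recorded at month 3 | Mean recorded time (months) | Events A | Median A (months) | Events B | Median B (months) |
|---|---|---|---|---|---|---|
| 0 | 72.7% | 3.82 | 0.926 | 2.86 | 0.926 | 2.86 |
| 10% | 65.5% | 4.04 | 0.906 | 3.09 | 0.833 | 3.36 |
| 25% | 54.6% | 4.36 | 0.876 | 3.45 | 0.694 | 4.36 |
| 50% | 36.4% | 4.91 | 0.827 | 4.12 | 0.463 | 7.35 |

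Example, f = 10%, case A: 0.693 × 4.04 / 0.906 = 3.09.

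**Step 4, when the estimate reaches 3.2 months.** Setting the Step 3 expression equal to 3.2 and solving for f gives about 15% in case A and about 7% in case B.

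**Step 5, separating the two causes.** The rise from 1.6 to 2.86 months is present at f = 0 and comes from the scan schedule. Only the further rise belongs to the threshold. With times dated to months 3 and 6, the simulated early-stopping probability at a true median of 1.6 months is already 0.004 or less at f = 0, so the threshold adds almost nothing to the futility decision.

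**The case against.** **The benchmark may use a similar rule.** The working treats 1.6 months as the median time to any new lesion. If the historical series also needed a sizeable nodule, that premise fails. This stands: the table shows how the rule acts, not the net bias. A reader might infer that the error always favours HIPEC. The documents do not support that against the 1.6-month benchmark, only against a definition that counts any new lesion.

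**The share f has no source.** This also stands. At 10% or 25% the Kaplan-Meier median stays at 3 months, and its jump to 6 reflects a schedule with only two scans.

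**The threshold has a visible reason.** Residual deposits up to 1 cm are allowed, so a margin above 1 cm helps to separate growth from what was left behind. That is fair for residual deposits. The rule makes no such distinction, however, and applies equally to nodules that are new.

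**The rule sits under off-study criteria.** Applying it to the primary endpoint is an inference. No other definition exists, so the gap needs closing on either reading.

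**Disease elsewhere.** A reader might infer that relapse outside the abdomen cannot count. Section 4.8.1 sets no anatomical limit, so an extra-abdominal nodule above 1.5 cm may already qualify. Smaller lesions and purely clinical progression do not.

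**New and residual nodules are hard to tell apart at month 3.** Section 4.5.5 schedules no scan between surgery and month 3. In the available text of Appendix 1 a CT/MRI mark falls under day 1, but so do the pregnancy test and the baseline audiology, so I read it as a pre-operative entry. This objection stands and shapes the fix.

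**Conclusion.** The point holds in a limited form. Followed as written, the plan scores a new nodule of 1.5 cm or less at month 3 as no relapse. Compared with counting any new lesion, this can only delay or remove events. Dating to month 6 is conditional: the nodule must exceed 1.5 cm by then and no unscheduled scan must intervene.

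The threshold's own contribution in case A is about 0.2 months at f = 10% (3.09 − 2.86), 0.6 at 25% (3.45 − 2.86) and 1.3 at 50% (4.12 − 2.86). It is larger in case B. These figures rest on the exponential model, a true median of 1.6 months for any new lesion, and an assumed f. A reader might credit the threshold with the whole distance from 1.6 months, or with disabling the futility rule. Both are mainly effects of the scan schedule. The damage from the threshold is to the reported median, and it is worth correcting because correction is cheap.

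**What to change.** For endpoint scoring only:

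- In 4.2.1, define relapse as an unequivocal new lesion at any site, or growth of a residual deposit documented at surgery.
- Record the size and site of every nodule on the scheduled scans.
- When a nodule of 1.5 cm or less at month 3 is confirmed by later growth, date relapse to its first appearance. Apply this in the final analysis, so that data already used in the continuous monitoring are not revised.
- Report the results under the 1.5 cm rule alongside.
- State the definition behind the historical 1.6 months and, where possible, apply one definition to both series.

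The recurrence wording in 4.4.1 and 4.8.1 differs, and the sponsor should reconcile it. No re-treatment or off-study rule is proposed here.

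The cost is wording, plus recording residual deposits at surgery and nodule sizes on scans already planned. The downside is small: with no scan scheduled between surgery and month 3, some small findings stay equivocal until the next scan.

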#### 4.9 Serious Adverse Event Reporting (SAE)

An adverse event or suspected adverse reaction is considered “serious” if, in the view of either the investigator or the sponsor, it results in any of the following outcomes:

- Death
- A life-threatening adverse drug experience – any adverse experience that places the patient, in the view of the initial reporter, at immediate risk of death from the adverse experience as it occurred. It does not include an adverse experience that, had it occurred in a more severe form, might have caused death.
- Inpatient hospitalization or prolongation of existing hospitalization
- A persistent or significant incapacity or substantial disruption of the ability to conduct normal life functions.
- A congenital anomaly/birth defect.

Important medical events that may not result in death, be life threatening, or require hospitalization may be considered a serious adverse drug experience when, based upon appropriate medical judgment, they may jeopardize the patient or subject and may require medical or surgical intervention to prevent one of the outcomes listed in this definition. Examples of such medical events include allergic bronchospasm requiring intensive treatment in an emergency room or at home, blood dyscrasias or convulsions that do not result in inpatient hospitalization, or the development of drug dependency or drug abuse (21 CFR 312.32).

- **Important medical events as defined above may also be considered serious adverse events. Any important medical event can and should be reported as an SAE if deemed appropriate by the Principal Investigator or the IRB.**
- All events occurring during the conduct of a protocol and meeting the definition of a SAE must be reported to the IRB in accordance with the timeframes and procedures outlined in "University of Texas M. D. Anderson Cancer Center Institutional Review Board Policy on Reporting Serious Adverse Events". Unless stated otherwise in the protocol, all SAEs, expected or unexpected, must be reported to the IRB, regardless of attribution (within 5 working days of knowledge of the event).
- **All life-threatening or fatal events**, that are unexpected, and related to the study drug, must have a written report submitted within 24 hours (next working day) of knowledge of the event to the IRB.
- **The MDACC "Internal SAE Report Form for Prompt Reporting" will be used for reporting to the IRB.**
- **Serious adverse events will be captured from the time the patient signs consent until 30 days after the last dose of drug. Serious adverse events must be followed until clinical recovery is complete and laboratory tests have returned to baseline, progression of the event has stabilized, or there has been acceptable resolution of the event.**
- **Additionally, any serious adverse events that occur after the 30 day time period that are related to the study treatment must be reported to the IRB. This may include the development of a secondary malignancy.**

**Reporting to FDA:**

- Serious adverse events will be forwarded to FDA by the IRB according to 21 CFR 312.32.

**It is the responsibility of the PI and the research team to ensure serious adverse events are reported according to the Code of Federal Regulations, Good Clinical Practices, the protocol guidelines, the sponsor's guidelines, and Institutional Review Board policy.**

The PI is responsible for ADR reporting. Adverse events will be documented according to the recommended adverse event recording guidelines for Phase II protocols as seen below.

Recommended Adverse Event Recording Guidelines					
Attribution	Grade 1	Grade 2	Grade 3	Grade 4	Grade 5
Unrelated	Phase I	Phase I	Phase I Phase II	Phase I Phase II Phase III	Phase I Phase II Phase III
Unlikely	Phase I	Phase I	Phase I Phase II	Phase I Phase II Phase III	Phase I Phase II Phase III
Possible	Phase I Phase II	Phase I Phase II Phase III	Phase I Phase II Phase III	Phase I Phase II Phase III	Phase I Phase II Phase III
Probable	Phase I Phase II	Phase I Phase II Phase III	Phase I Phase II Phase III	Phase I Phase II Phase III	Phase I Phase II Phase III
Definitive	Phase I Phase II	Phase I Phase II Phase III	Phase I Phase II Phase III	Phase I Phase II Phase III	Phase I Phase II Phase III

5.0 Human Subjects Protection

5.1 Rationale for use in children- Presently there is no standard treatment in children for tumors limited to peritoneal or retroperitoneal metastasis. In combination with other intravenous agents cisplatin has shown activity against various refractory, solid, pediatric tumors. In the treatment of many recurrent solid tumors, cisplatin is utilized as part of the intravenous regimen. Its use in HIPEC in adults has been promising. The PI has experience with this procedure in children and is the only one who will be performing the HIPEC procedure.

5.2 Informed Consent Benefits, Risks, Discomforts and Alternatives

5.2.1 Consent and Assent -- The investigational nature and objectives of this trial, the procedures involved and the attendant risks, discomforts, potential benefits and potential alternative therapies will be carefully explained to the adult patient (>=18 year old) or to the parent and when appropriate, the child, prior to treatment and prior to obtaining a signed informed consent as well as assent from the child. These discussions will take place in the clinic setting as well as the hospital. During the initial consultation, the parents are presented a forthright and detailed overview of the experimental nature of the procedure, its theoretical advantages and disadvantages

and an overview of the operative procedure and anticipated convalescence. The fact that the patient must undergo an operative procedure in order to receive therapy, without any assurance of benefit, the aggressive nature of the treatment and the likelihood of serious or potentially life threatening complications are presented. The adult patient ( $\geq 18$  year old) and/or parents will be informed that this therapy could make the patient or the child extremely ill and the risks of experiencing short or long term adverse effects from this treatment are high. The adult patient ( $\geq 18$  year old) and/or family is asked to review the informed consent document, encouraged to make notes, and a follow up discussion is scheduled either by phone or in person with the physician or nurse investigator and any additional questions will be answered prior to considering treatment on this protocol. At the time of consent and again the day of surgery, the family is reassured that participation in the trial is entirely voluntary and that they can withdraw or decide against treatment at any time without adverse consequences. Signed consent will be verified by the surgeon responsible for the care of the patient. A child life advocate will be a part of the informed consent process when the patient is a child.

5.2.2 Risks and Benefits- The potential benefit to a patient undergoing this therapy would be palliation in terms of preventing or delaying intra-abdominal tumor progression, which can be a devastating and painful source of symptoms and cause for demise. In addition, significant tumor response may extend survival. The risks of this protocol include those inherent to extensive abdominal surgery. This includes postoperative bleeding, wound infection, intra-abdominal abscess, wound dehiscence, enterocutaneous fistula, anesthetic complications and postoperative death. Also, toxicities of cisplatin therapy place the patient at risk. In addition, in the case of intra-abdominal catastrophe, patients may require re-operation.

5.2.3 Alternatives - Children dying of extensive peritoneal, retroperitoneal disease, or carcinomatosis, suffer with recurrent bowel obstructions, nausea, vomiting, abdominal pain, inability to pass stool, poor appetite and in late stages refractory ascites. Because there is presently no other treatment alternatives offered in this clinical scenario, aggressive treatment as a means of palliation and survival benefit, are justified. There have been many phase I and II trials in adults in which long term remissions after HIPEC in patients who were otherwise terminal, have been realized. Patients will be informed of other experimental chemotherapy options available.

## 6.0 Pharmaceutical Information

### 6.1 Cisplatin (cisplatin)

#### 6.1.1 General

Cisplatin will be purchased from the Pharmacy for the use in this trial. Commercial supply of FDA approved Cisplatin will be used. For drug information: Cisplatin Aqueous formulation 1mg/ml concentration (Various Vendors). Lot numbers will be tracked per drug accountability requirements. It will be purchased by an institutional grant for this protocol.

